12.0 PACKAGING AND LABELING OF INVESTIGATIONAL MEDICINAL PRODUCT

Medicinal product will be supplied by Spectrum Plasma in Fresenius Kabi individual 200 ml bags, containing--yFFP and 23-27 ml dextrose solution of citric acid, or 0.1% Riboflavin in normal saline as a control solution. Each bag will be blinded during administration by the study site.

Packaging and labeling will be completed in accordance with FDA regulations and Current Good Manufacturing Practice (CGMP). Spectrum Plasma is a FDA-AABB & CLIA registered, audited and accredited blood bank that will supply the investigation with FDA approved [21CFR640.30] plasma exclusively collected from

**INTRAVENOUS young FRESH FROZEN PLASMA (yFFP®) INVESTIGATIONAL TREATMENT FOR
PARKINSON'S DISEASE
PROTOCOL FOR CONTROLLED STUDY**

healthy, 18-25 year old sex-identified volunteer donors in full compliance to AABB and State of Texas regulations. yFFP is a registered trademark of Spectrum Plasma, Inc.

13.0 LABEL DESIGN FOR PRIMARY AND SECONDARY PACKAGING

IV bags will incorporate a masking structure that allows the placebo and yFFP to remain blinded to clinical staff and participants. Both the primary container (bag) and the secondary packing of the IV bags will be masked in an identical manner.

Example masking of the primary container (bag) and the secondary packing of the investigational medicinal product and the placebo.

14.0 PRESCRIPTION OF THE MEDICINAL PRODUCT

Medication will be prescribed by an authorized study physician according to the protocol, using a trial-specific prescription. The volume to be dispensed per patient will be calculated according to patient weight (dosing-schedule Table) and the site investigator will dispense the required number of bags.

Participants will be informed of potential adverse reactions and advised to seek medical help and contact the research team, if required.

Patients will carry cards with an emergency 24-hour emergency phone number.

Documentation of prescribing and dispensing study medication shall be maintained for study records in the patient file and a copy of all documents will be sent to the Trial Manager.

A specific prescription must be submitted to the Spectrum Plasma Blood Bank no later than the day prior to the patient's infusion.

**INTRAVENOUS young FRESH FROZEN PLASMA (yFFP®) INVESTIGATIONAL TREATMENT FOR
PARKINSON'S DISEASE
PROTOCOL FOR CONTROLLED STUDY**

15.0 DISPENSING AND DISTRIBUTION OF THE MEDICINAL PRODUCT

The study drug will be stored in a secure area with limited access within each site in the original shipping container until just prior to the infusion to ensure product temperature is maintained at -18°C or colder.

Supplies of study medications dispensed post-allocation will be blinded by the Spectrum Plasma Blood Bank and shipped according to centers SOP regardless if product is placebo or yFFP.

16.0 ADMINISTRATION OF THE MEDICINAL PRODUCT

If site prefers to run a slower infusion than described above, this will not be considered a protocol violation.

Patients may be offered diphenhydramine orally prior to starting the infusion.

Patients must be under continuous nurse observation during the infusion; in cases where no reduction of the infusion rate is required, the average infusion duration for a participant of 75 kg to 90 kg body weight is about 1.5 to 2 hours.

In the event that patients do not receive their entire first infusion, either due to having to stop early because of time constraints arising from long infusion duration with a low rate, or because side effects are intolerable even with the lowest infusion rate, they should still be offered the second infusion. Details of the amount infused should be recorded in the notes section of the infusion form.

Where the infusion cannot be tolerated, and the patient wishes to not receive additional infusion, the patient is withdrawn from further infusion, but follow-up data will be collected until the end of the study.

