7.0 STUDY DESIGN & METHOD

The study is a prospective double-blind placebo-controlled trial, designed to evaluate the safety and efficacy of intravenous young Fresh Frozen Plasma at 12.5 ml/kg in each of two doses, two days apart (25 ml/kg total).

Patients in the Placebo group will receive infusions of 0.9% Sodium Chloride with Vitamin B2 at a volume rate equal to that of yFFP 12.5 ml/kg in each of two doses, also two days apart.

Consecutive patients are alternately assigned to one of the two treatment study groups, labeled 'yFFP' or 'Saline' group. Because yFFP is in short supply,

**INTRAVENOUS young FRESH FROZEN PLASMA (yFFP®) INVESTIGATIONAL TREATMENT FOR
PARKINSON'S DISEASE
PROTOCOL FOR CONTROLLED STUDY**

the trial manager is free to change the strict alternate allocation sequence, according to the blood types of yFFP available.

Each participant's condition will be classified as mild to moderate. Patients above 2.5 on the Hoehn and Yahr scale will not be eligible for the trial.

The primary outcome is the change in sum of the UPDRS scales 1-3 in the yFFP group compared with the placebo group.

There will be one study site, a secondary care clinic specializing in neurology and infusions (Houston, Texas).

Study will include 20 patients with Parkinson's disease.

Blinding will be achieved by preparing both yFFP and placebo (0.1% Riboflavin in normal saline) solution into identical bags. The Riboflavin is added to achieve indistinguishable color when compared to the yFFP. Labels, barcoded numbers and expiration dates for both the active and saline placebo will be indistinguishable. All infusion bags will be masked.

For the time frame, study day 0 is defined as the day of treatment allocation. Baseline evaluation and laboratory testing will be done then. The first infusion will be scheduled at most two weeks later, and the second infusion will occur two days after the first.

Physician assessments, caregiver surveys and blood tests will be completed at 4-weeks, 12-weeks and 24 weeks, to explore the duration of yFFP - and unspecific treatment effects.

Definition of end of study

The end of the study will be the last participant's final contact at 24 weeks.

The study duration will be eight months from study set-up to analysis and closure. An interim report will be produced at the 12-week point.

Serious Adverse Events (SAE) will be monitored for 14-days after final dose of yFFP or until resolution.

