11.0 STUDY MEDICATION

Placebo

Matching placebo infusions will be supplied by the Spectrum Plasma Blood Bank for the infusion. These will be identical in appearance to the active infusions - they will be indistinguishable by color and labeling of the infusion.

yFFP infusion

The experimental intervention is 12.5 ml/kg intravenous Spectrum Plasma yFFP, per each of two infusions (25 ml/kg total), in combination with ongoing normal standard treatment.

For reported side effects of Spectrum Plasma yFFP infusion, please refer to AABB Circular of Information.

Contraindications include:

Absolute contraindications to the use of yFFP are documented intolerance to plasma or its components or selective deficiency of immunoglobulin A (IgA).

Relative contraindications are Heart failure or pulmonary edema.

Additional Cautions

Patients should avoid citrus and highly acidic fruits (example: strawberries, blueberries, loganberries, cranberries, currants, gooseberries, pineapple etc.) before and for a day after their last infusion, as patient may experience a reaction due to citrate.

Selection and timing of dose for each participant

Solutions will be available in 200 ml Spectrum Plasma yFFP infusion bags or matching placebo bags. Both bags will be masked prior to infusion.

In exceptional circumstances, where a randomized patient does not attend for the first infusion on day 1, delay of the first infusion up to day 5 is acceptable.

**INTRAVENOUS young FRESH FROZEN PLASMA (yFFP®) INVESTIGATIONAL TREATMENT FOR
PARKINSON'S DISEASE
PROTOCOL FOR CONTROLLED STUDY**

Data collection timelines remain the same, regardless of when infusions are received. Any patient who has not received his/her trial infusion by day 5, that is, before day 6, will be withdrawn and not given trial medication.

All patients who receive $\geq 80\%$ of the target dose will be included in the per-protocol analysis.

yFFP or placebo will be infused intravenously at an initial rate of not more than 2 ml/minute for 15 minutes. If well tolerated, the rate of administration may be increased to 10-15 ml/minute for the remainder of the infusion.

Infusion rate adjustments can be made if patients experience mild adverse clinical effects, reducing to 2 ml /minute in the first instance and further if required, while aiming for sufficient time to complete the entire infusion in a single day.

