29.0 WITHDRAWAL OF PARTICIPANTS

Study drug must be discontinued for the following:

1. The participant decides he/she no longer wishes to continue
2. Withdrawal is recommended by the Investigator or another clinician (for example, intercurrent illness during course of study or side effects from study drug)
3. The trial is terminated at the request of the Co-Investigator

Patients will be discontinued for the following:

**INTRAVENOUS young FRESH FROZEN PLASMA (yFFP®) INVESTIGATIONAL TREATMENT FOR
PARKINSON'S DISEASE
PROTOCOL FOR CONTROLLED STUDY**

Patient is randomized, but never receive any medicine (that is, the first infusion is never started - this is also termed 'non-compliance')

Participants have the right to withdraw from the study at any time and for any reason without providing a reason. The investigator also has the right to withdraw participants from the study if they consider that it is in the best interests of the participant. Should a participant decide to withdraw from the study, he/she will be asked to volunteer a reason for withdrawal but are at liberty not to state a reason.

Should a participant withdraw from study drug only, efforts will be made to continue to obtain follow-up data with the permission of the patient. Subjects who withdraw from treatment early will be encouraged to return to the study site for follow-up, providing that consent is not withdrawn.

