33.0 UNEXPECTED ADVERSE REACTIONS

Adverse event reporting will be in compliance with FDA. Most adverse drug reactions that occur in this study, whether serious or not, will be expected treatment-related side effects as FFP has a well-established side-effect profile and approximately 20% of all blood plasma transfused is from 18-25 year old donors (yFFP).

FFP can cause adverse reactions such as:

- Chills, headache, fever, vomiting, allergic reactions, nausea, arthralgia, low blood pressure and mild back pain, which may occur occasionally.

**INTRAVENOUS young FRESH FROZEN PLASMA (yFFP®) INVESTIGATIONAL TREATMENT FOR
PARKINSON'S DISEASE
PROTOCOL FOR CONTROLLED STUDY**

- Increase in serum creatinine level and/or acute renal failure have been observed.
- Very rarely, thromboembolic reactions, such as myocardial infarction, stroke, pulmonary embolism, and deep vein thromboses have occurred.

Details of further spontaneously reported adverse reactions include the following:

- Cardiac disorders: angina pectoris (very rare)
- General disorders and administrations site conditions: rigors (very rare)
- Immune system disorders: anaphylactoid shock (very rare), hypersensitivity (very rare)
- Blood pressure decreased (very rare)
- Musculoskeletal and connective tissue disorders: back pain (very rare)
- Respiratory, thoracic and mediastinal disorders: Dyspnea NOS (very rare);
or
- Vascular disorders: shock (very rare).

The adverse events reported above are expected in the sense that they are possible known side-effects of the study medication, but all reported instances of both serious and non-serious adverse events will be reported in this study.

During the trial, investigators will be made aware of any updates to the summary of product characteristics (SPC) but the protocol need not be amended every time there is a change unless it directly affects the study conduct. The source of accurate information regarding the active medication must always be the SPC and not the study protocol, and the above information is provided to reflect the situation at study start only.

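### The default offer of a second infusion after an intolerable first one has no exception for allergic-type plasma reactions, to which Section 11's absolute contraindication may apply

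*Combined protocol and SAP*

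**What the plan says.** Section 16 covers two ways in which infusion 1 may be left incomplete: it ran out of time at a low rate, or it was stopped for side effects. The instruction is the same for both. For the second it reads "because side effects are intolerable even with the lowest infusion rate, they should still be offered the second infusion". The only exit in that section depends on the patient: "Where the infusion cannot be tolerated, and the patient wishes to not receive additional infusion, the patient is withdrawn from further infusion".

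Section 11 states: "Absolute contraindications to the use of yFFP are documented intolerance to plasma or its components". It does not define documented intolerance. On handling reactions during the infusion it says: "Infusion rate adjustments can be made if patients experience mild adverse clinical effects", going down to 2 ml/minute and lower if needed.

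Section 33 lists the reactions to be expected from plasma: "Chills, headache, fever, vomiting, allergic reactions, nausea, arthralgia, low blood pressure and mild back pain, which may occur occasionally". It adds hypersensitivity and anaphylactoid shock as very rare.

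On timing, Section 7 says "the second infusion will occur two days after the first". Section 14 says "A specific prescription must be submitted to the Spectrum Plasma Blood Bank no later than the day prior to" the infusion.

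Section 29 makes discontinuation compulsory in several cases, one of which is "Withdrawal is recommended by the Investigator or another clinician (for example, intercurrent illness during course of study or side effects from study drug". It also gives the investigator a right to withdraw a participant in that participant's best interest.

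**The concern.** A stop for time and a stop for an intolerable reaction call for different decisions about re-dosing, and Section 16 gives them the same one. Most of the listed reactions, such as nausea or headache, create no difficulty: re-offering the infusion is a clinical choice and Section 11 does not bar it. An allergic-type reaction that a clinician attributes to plasma is different. The chart then holds a record that the patient did not tolerate plasma, while the written default is to offer more of it two days later.

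What is at stake is the safety of a small number of patients. Stopping depends on the patient declining or on a clinician deciding to recommend withdrawal. It does not depend on a check that the protocol requires.

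**Working it through.** No figure in the plan needs reproducing. The check compares the clauses and then sizes the dose at stake from the dosing table.

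**1. Who falls under both rules.** Section 16 applies to a patient with an incomplete infusion 1 and side effects intolerable at the lowest rate. Section 11 applies to a patient with documented intolerance to plasma. A patient meets both if the reaction was allergic-type, was recorded as plasma-related, and that record counts as documented intolerance. The third condition is an inference. Because Section 11 ties rate reduction to mild effects, the relevant case is a milder allergic-type reaction that persists or worsens at the lowest rate.

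**2. Whether another clause closes the gap.**
- Section 29: stopping is compulsory once a clinician recommends it, and the investigator may withdraw a patient. Nobody is required to review the patient before infusion 2.
- Section 28: withdraws patients with an unexpected new condition, but Section 33 classes the listed plasma reactions as expected.
- Section 36: a clinician assesses causality on-site, with no deadline and no link to dosing. Management follows local protocols, which cannot be seen here.
- Section 37: the convention of judging as though the patient had received the blood product is stated for SAEs only.
- Section 10: eligibility is checked at screening. No re-check between infusions is stated.
- Section 14: a study physician prescribes according to the protocol, and the protocol's default is to offer infusion 2.
- Section 33: the SPC is the source of product information. It cannot be seen here, and the clause does not say that Section 11 prevails over Section 16.

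**3. Timing.** With infusion 1 on day D, infusion 2 is on D+2 and its prescription is due by D+1. That leaves at most one day between infusion 1 and the last prescription date. No earliest date is given, so the text does not guarantee that the prescription follows the reaction.

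**4. Volume at stake** (dosing table in Section 11, 200 ml bags).

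| Weight band (kg) | Bags, infusion 1 | Bags, infusion 2 | Infusion 1 share of table volume |
|---|---|---|---|
| 45.5–55.4 | 4 | 3 | 4/7 = 57.1% |
| 55.5–65.4 | 4 | 4 | 4/8 = 50.0% |
| 65.5–75.4 | 5 | 4 | 5/9 = 55.6% |
| 75.5–85.4 | 6 | 5 | 6/11 = 54.5% |
| 85.5–95.4 | 6 | 6 | 6/12 = 50.0% |
| 95.5–105.4 | 7 | 6 | 7/13 = 53.8% |
| 105.5–115.4 | 7 | 7 | 7/14 = 50.0% |
| 115.5–125.4 | 8 | 8 | 8/16 = 50.0% |
| 125.5–135.4 | 8 | 9 | 8/17 = 47.1% |

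Infusion 2 is 3 × 200 = 600 ml to 9 × 200 = 1,800 ml. Per kg, over eligible weights (45.5 to 130 kg), the highest is 800/55.5 = 14.4 ml/kg and the lowest is 800/75.4 = 10.6 ml/kg.

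**5. Per-protocol consequence of withholding infusion 2.** Section 11 requires at least 80% of the target dose. A complete infusion 1 is 47% to 57% of table volume. Against 25 ml/kg it is at most 800/(25 × 45.5) = 70.3% and at least 1,400/(25 × 115.4) = 48.5%. All are below 80%, so a patient without infusion 2 leaves the per-protocol set.

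That loss is not wholly due to the change, because infusion 1 was incomplete by definition. With a 50/50 bag split, a full infusion 2 reaches 80% of table volume only if the fraction x of infusion 1 satisfies 0.5 + 0.5x ≥ 0.8, that is x ≥ 0.6. Patients stopped earlier would have missed the threshold anyway.

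**The case against.** The strongest reply is that the clauses can be read together. Section 16 only says the infusion should be offered, and the patient may refuse. Section 11's contraindication is absolute, and Section 29's stop on a clinician's recommendation is compulsory, with side effects as its own example. A sensible physician would let those override a default. Documented intolerance may also mean a known history, not a reaction logged during the trial. Section 16 requires continuous nurse observation and allows oral diphenhydramine beforehand, and Section 14 puts a physician's prescription before each infusion. An inclusive default is useful too, since it keeps patients from being withdrawn for nausea or a late finish.

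Much of this stands. It narrows the point to one kind of reaction and shows real protection. It does not supply a required review, an exception in Section 16, or a statement of which section prevails.

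Three stronger readings are tempting, and the documents do not support them:
- *That the plan directs re-infusion after anaphylactoid shock.* The rate-reduction step is written for mild effects, and nothing suggests Section 16 had shock in view.
- *That any intolerable side effect creates a conflict.* Section 11 concerns intolerance to plasma or its components. Headache or nausea need not be that.
- *That reporting is too slow to matter, because the sponsor may hear of a non-life-threatening SAE only after 3 days.* The sponsor has no stated role in the infusion 2 decision. Section 37 has the Co-Investigator and Trial Manager told within 24 hours of the event becoming known.

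**Conclusion.** The point holds in a limited form. Section 16's unqualified default is inconsistent with Section 11 for a patient with an allergic-type reaction recorded as plasma-related, provided that record counts as documented intolerance. I think that is the natural reading, but it remains an inference, and confidence is medium for that reason.

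A true contraindication can arise only among the 10 patients assigned to yFFP. The documents describe frequency only in words, so no probability is claimed. A reader might infer that nobody can stop the second infusion; Section 29 rules that out. The defect is that stopping is left to discretion, against a written default that points the other way. It is a patient-safety wording fault worth correcting, and it does not affect the sample size.

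**What to change.** Split the Section 16 sentence in two.

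1. Infusion 1 stopped for time: keep the offer of infusion 2.
2. Infusion 1 stopped for intolerable side effects: offer infusion 2 only if a blinded study physician, judging as though the patient had received plasma, documents beforehand that the reaction was neither allergic-type nor suspected plasma intolerance and that re-dosing is safe. Otherwise discontinue infusions under Sections 11 and 29 and continue follow-up to week 24.

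Add one sentence stating that Section 11 contraindications override Section 16.

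The cost is a one-paragraph amendment, brief training at the single site, and one documented review within two days per affected patient. Because the judgement is blinded, some placebo patients will also lose their second infusion. The patients stopped will be outside the per-protocol set, though some would have been anyway, and their follow-up data are still collected. Section 5 lists the trial as closed in January 2019. If dosing is complete, the change applies to any reuse of the protocol, and the sponsor can check the infusion logs for patients re-dosed after a reaction-related stop.

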17.0 SAFETY MONITORING

The blood tests listed below in Section 18.0 will be done at baseline and at 4,12, and 24 weeks. Additional blood monitoring is only required for the protocol in response to adverse events.

18.0 ROUTINE HEMATOLOGY

Routine hematology includes the following:

- White blood cell and differential count (eosinophils, basophils, neutrophils, lymphocytes and monocytes)
- Red blood cell and indices (PCV, MCV, MCH, MCHC)
- Hemoglobin
- Platelets

**INTRAVENOUS young FRESH FROZEN PLASMA (yFFP®) INVESTIGATIONAL TREATMENT FOR
PARKINSON'S DISEASE
PROTOCOL FOR CONTROLLED STUDY**

- Serum IgA
- Serum IgM
- Serum IgG.
- C-reactive Protein

Biochemistry

Routine biochemistry includes:

- Sodium
- Potassium
- Urea
- Serum creatinine
- ALT, AST, GGT, Bilirubin.

19.0 PREGNANCY

Pregnancy status will be verified using blood pregnancy testing at baseline for female patients of childbearing potential and urine pregnancy testing at visit --- if patient is receiving yFFP.

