3.0 DEFINITIONS

FFP: fresh frozen plasma, not necessarily from a young donor

SAE: serious adverse event

SOP: standard operating procedure

yFFP: fresh frozen plasma from a young (18 – 25 year old), sex-identified donor

**INTRAVENOUS young FRESH FROZEN PLASMA (yFFP®) INVESTIGATIONAL TREATMENT FOR
PARKINSON'S DISEASE
PROTOCOL FOR CONTROLLED STUDY**

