20.0 ALLOCATION

Identification and allocation of patients

A patient identification number will be assigned after consent has been signed.

Patients will be allocated to placebo or yFFP (ratio 1:1) by Trial Manager.

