38.0 PREGNANCY

Should a trial participant become pregnant during the trial, she will be immediately withdrawn from study treatment, and the pregnancy will be followed up until outcome. The need to unblind will be considered on a case-by-case basis. Pregnancy will be reported as a serious adverse event. Data collection at the planned scheduled follow-up timeline must continue, unless the patient is unwilling to provide further data.

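### Section 19.0 ties the follow-up urine pregnancy test to receipt of the active product, which blinded staff cannot apply without knowing the arm and which, applied literally, reveals it

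*Combined protocol and SAP*

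**What the plan says.** Section 19.0 sets two pregnancy checks. The first is "blood pregnancy testing at baseline for female patients of childbearing potential", with no reference to treatment group. The second is "urine pregnancy testing at visit --- if patient is receiving yFFP". The visit number is left as dashes, and the condition on the test is "if patient is receiving yFFP".

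The term that carries the condition is defined in Section 3.0: "yFFP: fresh frozen plasma from a young (18 – 25 year old), sex-identified donor". It names the active product and does not cover the saline and riboflavin placebo.

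Section 7.0 states: "The study is a prospective double-blind placebo-controlled trial". Section 13.0 describes masking that "allows the placebo and yFFP to remain blinded to clinical staff and participants". Under Section 20.0 the allocation is made by the Trial Manager: "Patients will be allocated to placebo or yFFP (ratio 1:1) by Trial Manager".

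Section 38.0 says of a pregnancy during the trial, without distinguishing the groups: "Pregnancy will be reported as a serious adverse event". Any resulting unblinding is to be decided case by case. Section 37.0 has every serious adverse event assessed as if the patient had received the blood product, and it shares event information in a way meant to avoid revealing the arm.

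**The concern.** A procedure carried out on the patient at a visit should not depend on which arm she is in if the people carrying it out are meant not to know. Section 19.0 makes it depend on exactly that.

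Two things are at stake:

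- **The blind.** The primary outcome is the change in the sum of UPDRS scales 1 to 3, and Section 7.0 relies on physician assessments and caregiver surveys at follow-up. Ratings of this kind can be influenced by knowledge of treatment. The protocol takes care to match the colour, labels and bags, and a test given in one arm only would bypass those measures for the women it covers.
- **Even ascertainment.** Adverse events are a secondary outcome (Section 8.0). A reportable event that is looked for by test at follow-up in one arm only is not ascertained equally.

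**Working it through.** The plan gives no figure to reproduce. The check is to set the provisions side by side and follow the rule through.

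**Step 1: does the condition depend on the arm?** Yes, on the defined term. Section 3.0 limits yFFP to young-donor plasma, and Sections 2.0, 7.0 and 20.0 each contrast it with the placebo. The baseline half of the same sentence carries no such condition.

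**Step 2: who could apply it?** Sections 7.0 and 13.0 keep clinical staff and participants blinded. Section 20.0 puts allocation with the Trial Manager. The public text provides no unblinded tester, no sham test and no matching test in the placebo group.

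**Step 3: what could the site do with a woman of childbearing potential?**

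| Site action | Arm revealed? | Section 19.0 followed? |
|---|---|---|
| Is told the arm and applies the rule | Yes | Yes |
| Tests every such woman in both groups | No | No: placebo patients tested outside the rule |
| Tests none | No | No: yFFP patients not tested |

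The rule as written is followed only in the first row. There, among women of childbearing potential:

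- P(yFFP | test done) = 1
- P(placebo | test not done) = 1

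The omission is therefore as informative as the test. The disclosure reaches staff, who hold the protocol. It reaches the patient only if she knows the rule.

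**Step 4: how many women?** Section 9.0 sets entry at age 45 or above, but it expressly allows for premenopausal women who could become pregnant, subject to birth control. The documents give no sex or menopausal mix. Taking 0 to 2 of 20 as an assumption:

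- Share of the trial: 0/20 = 0% to 2/20 = 10%.
- Each such woman as a share of her arm (Section 2.0, 10 per arm): 1/10 = 10%.

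**Step 5: is arm-dependent handling the protocol's general approach?** No. Section 37.0 evaluates serious adverse events as though every patient were on the active product, and Section 38.0 does not make unblinding automatic in pregnancy. Section 19.0 is out of line with both.

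**The case against.** The strongest reply is that the wording is loose and no arm-specific test was meant. Section 7.0 times serious adverse event monitoring from the final dose of yFFP, while Section 34.0 gives the same 14-day window from the end of study drug. Section 7.0 cannot sensibly mean that events are monitored in one arm only. On that usage, the Section 19.0 clause may simply mean a visit at which an infusion is given. This is plausible, and Sections 37.0 and 38.0 fit it. It does not cure the text: staff have to follow what is written, the defined term points the other way, and the same edit is needed on either reading.

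The second reply is that the practical effect may be nil. With entry at 45 or above and birth control required, there may be no affected woman. That stands as a limit on size. The ascertainment point is also modest, since Section 38.0 requires any known pregnancy in either arm to be reported and followed to outcome.

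A reader might infer that each woman of childbearing potential is certain to be unblinded before the 24-week primary rating. The documents do not support that:

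- The visit is blank, so the test cannot be placed before the rating.
- Disclosure is not certain, because blinded staff might test everyone or no one, and nothing instructs the Trial Manager to tell the site the arm.
- The patient does not learn her arm from the test alone.

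**Conclusion.** The concern holds as a conflict in the text. Section 19.0 makes a follow-up procedure depend on receipt of the active product, against the blinding in Sections 7.0 and 13.0 and the arm-neutral event handling in Section 37.0. Either blinded staff cannot apply the rule, or applying it reveals the arm to those who know it and confines follow-up pregnancy testing to one group.

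The size is small and possibly zero: 0 to 2 of 20 patients, on an assumption the documents neither confirm nor exclude. Where there is an affected woman she is 10% of her arm. Any effect on the primary comparison also depends on a visit time that is not given. The conclusion rests on reading yFFP as Section 3.0 defines it. If the study infusion was meant, what remains is a wording error to correct. The point is worth acting on because the edit is so cheap, and it does not suggest that the primary result is compromised.

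**What to change.** Reconcile Section 19.0 with Sections 7.0, 13.0 and 37.0 by removing the arm condition, so that whatever follow-up pregnancy test is scheduled applies identically to women of childbearing potential in both groups. The blank visit is a separate gap that the sponsor should fill in the same edit; which visit it should be is not a matter for this review.

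Section 5.0 lists the trial as closed in January 2019. For visits already completed, the useful step is to record how the clause was applied, whether any woman was covered by it, and whether anyone learned an allocation through it. The text should be corrected before any reuse.

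The cost is one clause, plus extra urine tests in the placebo arm. On the assumption of 0 to 2 women in the whole trial, that is at most 2 extra tests for each visit at which the test is scheduled.
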